9.2 Materials and Supplies

Pembrolizumab drug product is available in 2 -dosage forms: ~~is~~ a white to off-white lyophilized powder, 50 mg/vial, and a liquid, 100 mg/vial, both in Type I glass vials intended for single use only.

- Pembrolizumab ~~powder~~ Powder for solution ~~Solution for infusion~~ Infusion, 50 mg/vial, is a lyophilized powder that is reconstituted with sterile water for injection prior to use. Pembrolizumab is formulated with L-histidine as buffering agent, polysorbate 80 as surfactant, sucrose as stabilizer/tonicity modifier, and may contain hydrochloric acid and/or sodium hydroxide for pH adjustment (if necessary).
- Pembrolizumab Solution for Infusion 100 mg/vial is a liquid, manufactured fully formulated with L-histidine as a buffering agent, polysorbate 80 as a surfactant, and sucrose as a stabilizer/tonicity modifier.

Both ~~The~~ pembrolizumab product dosage forms are ~~is~~ stored under refrigerated conditions (2°C to 8°C) ($36\text{-}46^{\circ}\text{F}$) and protected from light. Refer to pembrolizumab IB for detailed storage information.

Leo Document ID = 31dd044a-cd95-424c-a86f-4ce3cecc795e

Approver: PPD
Approval Date & Time: 17-Sep-2018 14:38:09 GMT
Signature meaning: Approved

Approver: PPD
Approval Date & Time: 17-Sep-2018 14:39:24 GMT
Signature meaning: Approved

Changes from Statistical Analysis Plan Version 1.0

1. Part C has been added according to the protocol JFCQ(a)
2. The timing of Primary analysis and final analysis for Parts A and B have been updated according to the protocol JFCQ(a)
3. Events of Clinical Interest (ECIs) have been updated according to the protocol JFCQ(a)
4. Interim efficacy analyses have been added according to the protocol JFCQ(a)
5. Various sections modified according to the new TAFFY standard TFL shells

Changes from Statistical Analysis Plan Version 2.0

1. The final analysis has been removed per protocol update
2. Interim efficacy analyses for squamous patients has been added

4. Study Objectives

4.1. Primary Objective

This study is divided into 3 parts:

Part A: to investigate safety and tolerability of pembrolizumab 200 mg Q3W when combined with necitumumab administered at the doses of 600 mg and 800 mg on Days 1 and 8 of 21-day cycles in patients with Stage IV NSCLC (all histologies) as measured by number of patients with a dose-limiting toxicity (DLT) during Cycle 1.

Part B: to evaluate the efficacy of necitumumab in combination with pembrolizumab in terms of overall response rate (ORR) by Response Evaluation Criteria in Solid Tumors Version 1.1 (RECIST 1.1) in patients with Stage IV NSCLC of squamous and nonsquamous histology.

Part C: to investigate safety and tolerability of pembrolizumab 200 mg Q3W when combined with necitumumab administered at the recommended dose from Part A in Japanese patients with Stage IV NSCLC of squamous and nonsquamous histology as measured by number of patients with a DLT during Cycle 1.

4.2. Secondary Objectives

The secondary objectives of the study are as follows:

Part A and C:

- to investigate the safety profile as assessed by significant clinical and laboratory events of necitumumab in combination with pembrolizumab
- to determine the ORR (by RECIST 1.1)
- to determine pharmacokinetics (PK) of necitumumab in presence of pembrolizumab
- to determine the immunogenicity of necitumumab in presence of pembrolizumab

Part B:

To demonstrate the feasibility of combining necitumumab with pembrolizumab at the recommended doses by:

- investigating the safety profile as assessed by clinical and laboratory significant events
- determining disease control rate (DCR), duration of response (DOR), progression-free survival (PFS) by RECIST 1.1, and overall survival (OS)
- determining PK of necitumumab in the presence of pembrolizumab
- determining the immunogenicity of necitumumab in the presence of pembrolizumab

4.3. Exploratory Objectives

- to investigate biomarkers, including pharmacodynamics markers, related to necitumumab, pembrolizumab, EGFR, immune cells/function, and disease state, and correlate these markers to clinical outcome
- to assess immune-related (ir)ORR, irDCR, irDOR, and irPFS by adapted RECIST 1.1 (immune-related RECIST [irRECIST])

5. A Priori Statistical Methods

5.1. Determination of Sample Size

A total of approximately 78 patients for either Part A, Part B or Part C will be enrolled. Part A requires up to 12 treated patients (3-6 for Cohort 1 and 6 for Cohort 2). Patients with squamous and nonsquamous NSCLC from Part A who received the recommended necitumumab dose for Part B will also be analyzed together with Part B. In Part C, approximately 6-12 Japanese patients will be enrolled and treated with necitumumab at the recommended dose from Part A in combination with pembrolizumab.

The primary analysis of the Part A and Part B will take place approximately 6 months after the last patient evaluable for Part B portion of the study has been enrolled. The primary Part B outcome variable in this study will be ORR. The Part B statistical null hypothesis states that the true ORR associated with the regimen of necitumumab and pembrolizumab is 20%, whereas the research hypothesis states that the true ORR associated with the combination regimen is 35%.

If the research hypothesis of a 35% ORR is true, there is an 83% chance of rejecting the null hypothesis. If the null hypothesis of a 20% ORR is true, then there is at most a 10% chance of rejecting the null hypothesis. Therefore, the sample size of 54 evaluable patients in Part B has a nominal one-sided alpha level of 0.10, with statistical power of 83%.

The analysis of Part C will take place approximately after all the patients from Part C have completed 8 cycles or discontinued early. At the same time, some of the efficacy of part B may be updated, where appropriate.

5.2. General Considerations

In Part A, data will be summarized by assigned necitumumab + pembrolizumab dose levels unless stated otherwise. Patients with squamous and nonsquamous NSCLC from Part A who received the recommended Phase II dose will also be analyzed together with Part B. They are:

- NSCLC squamous at the recommended Phase 2 dose: Part A patients with squamous NSCLC and treated at the recommended Phase 2 doses of necitumumab and pembrolizumab + Part B patients with squamous NSCLC
- NSCLC nonsquamous at the recommended Phase 2 dose: Part A patients with nonsquamous NSCLC and treated at the recommended Phase 2 doses of necitumumab and pembrolizumab + Part B patients with nonsquamous NSCLC

Part C patients will be summarized separately.

The following populations will be defined for this study:

- **All entered population:** anyone who signed the informed consent will be included in this population.
- **Safety population:** all patients who have received any amount of study drug [necitumumab, and/or pembrolizumab]

- **Evaluable population:** To be evaluable for the study, these patients must meet the following criteria:
 - (1) The patient has received at least 1 dose each of necitumumab and pembrolizumab.
 - (2) The patient has a complete radiographic assessment at baseline.

An evaluable patient for Part B will include any patient enrolled in Part A with squamous and nonsquamous NSCLC and treated at the recommended Phase 2 doses of necitumumab and pembrolizumab, and patients who entered strictly to Part B.

Unless otherwise specified, for continuous variables, summary statistics will include number of patients, mean, median, standard deviation, minimum, and maximum. Categorical variables will be summarized using frequency and percentages.

- **Age (years):** $(\text{Informed Consent Date} - \text{Date of Birth} + 1)/365.25$, if only year of birth is collected, see Section 5.3 for date imputation.
- **Missing Data:** All analyses and descriptive summaries will be based on the observed data. Unless otherwise specified, missing data will not be imputed or “carried forward.”
- **Baseline Measurement:** Unless otherwise specified, the last non-missing measurement prior to the first dose of study drug will serve as the baseline measurement.
- **Study Day:** Study day is calculated as assessment date – first dose date + 1 day if the assessment is done on or after the first dose day. If the assessment is done prior to the first dose day, study day will be calculated as assessment date – first dose date. Date of first dose is defined as study day 1.
- **Duration:** Duration is calculated as:
 - Duration (days): $(\text{End Date} - \text{Start Date} + 1)$
 - Duration (weeks): $(\text{End Date} - \text{Start Date} + 1)/7$
 - Duration (months): $(\text{End Date} - \text{Start Date} + 1)/30.4375$ (Days in months = $(1/12) \times \text{average number of days in a year.}$)
 - Duration (years): $(\text{End Date} - \text{Start Date} + 1)/365.25$ (Average days in a year = 365.25, reflecting the Julian Year of three years with 365 days each and one leap year of 366 days.)
- **Time-to-event:** The event or censoring time (days) is calculated as:
Date of event/censoring – Date of first dose of study drug + 1

5.3. Handling of Dropouts or Missing Data

Dates missing the day or both the day and month of the year will adhere to the following conventions:

- The missing day of onset of an adverse event (AE) or start date of a concurrent therapy will be set to:

- first day of the month that the event occurred, if the onset yyyy-mm is after the yyyy-mm of first study treatment
- the day of the first study treatment, if the onset yyyy-mm is the same as yyyy-mm of the first study treatment
- the date of informed consent, if the onset yyyy-mm is before the yyyy-mm of the first treatment.
- The missing day of resolution of an AE or end date of a concurrent therapy will be set to:
 - the last day of the month of the occurrence. If the patient died in the same month, then set the imputed date as the death date.
- If the onset date of an AE or start date of a concurrent therapy is missing both the day and month, the onset date will be set to:
 - January 1 of the year of onset, if the onset year is after the year of the first study treatment
 - the date of the first treatment, if the onset year is the same as the year of the first study treatment
 - the date of informed consent, if the onset year is before the year of the first treatment
- If the resolution date of an AE or end date of a concurrent therapy is missing both the day and month, the date will be set to:
 - December 31 of the year of occurrence. If the patient died in the same year, then set the imputed date as the death date
- If date is completely missing, then no imputation will be done and the event will be considered as treatment emergent unless the end date rules out the possibility.

For initial diagnosis date, the following conventions will be used for imputing partial dates:

- If only the day of the month is missing, the 15th of the month will be used to replace the missing day.
- If both the day and the month are missing, “Jul 1” will be used to replace the missing information.

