12.2.7. Analyses of Efficacy

In addition to the analyses described in Section 12.1, this section provides additional details of planned efficacy analyses. For time-to-event variables, the Kaplan-Meier method will be used to estimate parameters (for example, medians, quartiles, 6 months, and 1-year event rates). See also the SAP for additional details.

ORR: The denominator of ORR includes each evaluable patient. The numerator includes those patients counted in the denominator with a best overall tumor response of PR or CR.

DCR: Using the same denominator as for ORR, the numerator of the DCR includes those patients counted in the denominator with a best tumor response of SD, PR, or CR.

DOR: The DOR is defined only for responders (patients with a confirmed CR or PR, as defined in Section 10.1.1). It is measured from the date of first evidence of a confirmed CR or PR to the date of objective progression or the date of death due to any cause, whichever is earlier. If a responder is not known to have died or have objective progression as of the data inclusion cutoff date, DOR will be censored at the date of the last complete objective progression-free disease assessment.

PFS: The PFS time is measured from the date of first dose to the date of objective progression or the date of death due to any cause, whichever is earlier. The censoring is taken in the following order:

- if a patient does not have a complete baseline disease assessment, then the PFS time will be censored at the first dose date, regardless of whether or not objectively determined disease progression or death has been observed for the patient; otherwise,
- if a patient is not known to have died or have objective progression as of the data inclusion cutoff date for the analysis, the PFS time will be censored at the last complete objective progression-free disease assessment date.

OS: OS duration is measured from the date of first dose to the date of death from any cause. For each patient who is not known to have died as of the data-inclusion cutoff date for a particular analysis, OS will be censored for that analysis at the last known alive date. ORR, DCR, DOR, and PFS will be assessed based on RECIST 1.1.

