5.5.6.1. Overall Survival (OS)

Overall survival duration is measured from the date of first dose of study drug (necitumumab and/or pembrolizumab) to the date of death from any cause. For each patient who is not known to have died as of the data-inclusion cut-off date for a particular analysis, OS will be censored for that analysis at the date of last contact prior to the data inclusion cut-off date (contacts considered in the determination of last contact date include adverse event date, lesion assessment date, visit date, and last known alive date).

An exploratory analysis on the potential prognostic factors may be performed. The following potential prognostic factors may be considered:

1. histology (squamous versus nonsquamous)
2. age (<70 versus ≥70)

3. number of sites of metastases (>2 versus ≤2)
4. ECOG PS (0 versus >0)
5. gender (females versus males)
6. baseline sum of target lesions (as a continuous variable)
7. baseline hemoglobin (as a continuous variable)
8. baseline leukocytes (as a continuous variable)
9. baseline platelets (as a continuous variable)

Each factor is assessed through separate univariate Cox proportional hazard models, and then all factors are incorporated into the multivariate Cox proportional hazard model. This exploratory analysis may be performed on OS and PFS.

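### SAP 5.3 sets a partial AE onset date to the first-dose date without checking the recorded end date, so an AE known to have resolved before dosing is counted as treatment-emergent

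*SAP*

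**What the plan says.** SAP 5.3 has three onset rules that matter here.

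- Day missing, onset in the month of first dose: onset becomes "the day of the first study treatment, if the onset yyyy-mm is the same as yyyy-mm of the first study treatment".
- Day and month missing, onset in the year of first dose: onset becomes "the date of the first treatment, if the onset year is the same as the year of the first study treatment".
- Date completely missing: nothing is imputed, and "the event will be considered as treatment emergent unless the end date rules out the possibility".

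Only the third rule refers to the end date. For a partial end date with day and month missing, the imputed value is "December 31 of the year of occurrence. If the patient died in the same year, then set the imputed date as the death date". A missing day alone goes to month end, with the same replacement by the death date.

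SAP 5.6.2 defines a TEAE as an event that first occurred or worsened from first dose to 30 days after last dose, plus later related SAEs. Protocol 10.2.1 has sites record AEs once consent is signed, and Table JFCQ.10.2 lists all AEs for the baseline period, which the Synopsis allows to last up to 21 days. Pre-dose AEs are therefore in the database.

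For OS, SAP 5.5.6.1 censors at the last contact before the data cut-off and says that "contacts considered in the determination of last contact date include adverse event date, lesion assessment date, visit date, and last known alive date". Protocol 12.2.7 says "OS will be censored for that analysis at the last known alive date".

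**The concern.** A partly known onset date is handled less accurately than an unknown one. If the onset is blank and the end date precedes dosing, the event is correctly left out of the TEAE tables. If the site supplies the month, and it is the first-dose month, the same event is put in.

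The result is a record whose onset falls after its resolution, and a pre-treatment event reported as emerging on treatment. TEAE incidence by preferred term, grade and AESI category is the main safety output, and safety is a stated objective in all three parts.

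**Working it through.** The plan gives no figure for this point, so there is none to reproduce. The check is to apply the rules literally to a record.

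**The rule on one record (illustrative dates).** First dose 20 March; AE onset March, day missing; recorded end 10 March.

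1. Onset month equals first-dose month, so imputed onset = 20 March.
2. SAP 5.2 duration = end − start + 1 = 10 − 20 + 1 = −9 days, an impossible value.
3. Imputed onset is on or after first dose, so the event meets the TEAE definition.
4. With the end-date condition already written for blank dates, 10 March is before 20 March and the event is not a TEAE.

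A year-only onset in the first-dose year gives the same outcome. An onset in an earlier month (or an earlier year, if only the year is known) goes to the consent date and is not affected.

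**How much of screening is exposed.** Assume a 21-day window, onset uniform over it, and first dose on a uniformly distributed day d = 1 to 30. The share of screening days in the first-dose month is the mean of min(21, d − 1)/21.

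- Sum for d = 1 to 22: 0 + 1 + … + 21 = 231.
- Sum for d = 23 to 30: 8 × 21 = 168.
- Share = (231 + 168)/(30 × 21) = 399/630 = 0.633.

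Enumerating two calendar years of first-dose dates gives 0.64. The baseline schedule in Attachment 1 marks AE collection in the 14-day column; a 14-day window gives about 0.75. These are shares of days on which a pre-dose onset could meet the rule.

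**Effect of one record.** Take the planned 54 Part B patients as denominator. One misclassified patient with no true on-treatment event of that term adds 1/54 = 1.9 percentage points to its incidence. If the 6 patients of Part A Cohort 2 are pooled, it adds 1/60 = 1.7 points.

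**OS wording (secondary).** SAP 5.5.6.1 does not say whether the AE date is a start or an end, observed or imputed. To see what the open reading would allow, take first dose 21 March 2016, last real contact 15 June 2016, an AE end recorded only as 2016, a patient not known to have died, and an assumed cut-off of 21 June 2017.

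- Censoring at real contact: 86 + 1 = 87 days.
- Censoring at the imputed 31 December 2016: 87 + 199 = 286 days.
- With a cut-off of 1 October 2016, 31 December falls after the cut-off and is excluded, so nothing changes.

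**The case against.** The best defence is that first-dose imputation is deliberately conservative: when timing is unclear, count the event as treatment-emergent so that no safety signal is hidden. AEs are collected on Days 1 and 8 of each cycle, so dates with a missing day should be uncommon. A listing of all AEs is planned, Protocol 11 specifies data edits, and Protocol 8.2 calls the outcome hypothesis-generating.

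Much of this stands. The direction is cautious and the number of records is likely to be small. But caution is an argument for cases where timing is unknown. Here a recorded end date settles it, and the SAP accepts that reasoning for blank dates. Data edits on collected fields need not catch a contradiction that imputation creates later.

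A reader might infer three stronger things that the documents do not support.

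- **That SAP 5.3 checks no other dates.** It does: imputed end dates give way to the death date, and completely missing dates are tested against the end date.
- **That 63% of screening AEs are misclassified.** That figure is a share of days under assumed uniformity. Misclassification also needs a partial onset and an end date known to precede dosing, and neither frequency is given.
- **That OS is censored at imputed dates, biasing the survival curve upward and contradicting the protocol.** SAP 5.5.6.1 never says imputed dates count as contacts. SAP 5.2 defaults to observed data unless otherwise specified, and contacts must precede the cut-off. The SAP list includes the protocol's last known alive date, and Protocol 12.2.7 refers to the SAP for detail. No conflict is shown; the wording is only silent.

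**Conclusion.** The TEAE point holds as a small defect in a stated rule. Read literally, SAP 5.3 classes an AE known to have ended before dosing as treatment-emergent whenever its partial onset falls in the first-dose month, or in the first-dose year if the month is also missing. It applies the obvious safeguard only to blank dates.

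The total size is unknown because the documents do not give the number of partial dates. It is probably a handful of records at most, each worth under two percentage points on a single term, and always in the direction of over-counting TEAEs. The conclusion rests on the rule being programmed as written; a programmer might add the check unprompted, but the SAP does not ask for it. The primary ORR test uses no AE dates and is unaffected.

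The OS wording is a request for clarification, not a demonstrated bias. For an imputed 31 December to matter, four things must coincide: imputed end dates are treated as contacts, the end date is year-only, the patient is not known to have died, and the cut-off falls after that 31 December.

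**What to change.** In SAP 5.3, extend the end-date condition now attached to completely missing dates to partial onset dates. An imputed onset may not fall after a recorded complete end date, and an AE whose recorded end date precedes first dose is not treatment-emergent. In practice the imputed onset becomes the earlier of the first-dose date and the recorded complete end date. Keep the first-dose default in every other case, including an end date that is missing or falls on or after first dose.

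In SAP 5.5.6.1, add that an AE date counts as a last contact only if it is complete and observed, so that imputed month-end and 31 December dates are excluded.

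The cost is two sentences and a minor change to the date-derivation program. No data collection, sample size or primary analysis changes.

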5.4. Patient Disposition

A detailed description of patient disposition will be provided. It will include a summary of the number and percentage of patients never treated, still under treatment (that is, have not completed the End of Treatment [EOT] visit) at data cut-off date will be summarized. Patients discontinued from treatment will be presented by reason.

The number and percentage of patients with any important protocol violation will be summarized overall and by type of violation. The pre-defined important protocol violations are listed in below; in addition, any other protocol violations reviewed by CRP and deemed to be important protocol violations will be included in the summary.

- Patient failed to meet study inclusion/exclusion criteria
- Study treatment continued after progressive disease (PD) occurred
- Patient received concurrent prohibited therapy (Listing to identify Anatomical Therapeutic Chemical (ATC) codes is to be provided for medical review) while receiving study treatment.
- Necitumumab continued after Grade 3-4 infusion reaction occurred (as defined by dictionary term “Infusion related reaction”)
- Post-baseline tumor assessments use different methods than baseline assessment
- Actual doses of study drug was more than 10% greater than protocol defined dose (800 mg for necitumumab, 200mg for Pembrolizumab), at any of dose administration
- Patient started next cycle less than 18 days later after Day 1 of the most recent treatment cycle
- Patient received more than 2 dose reductions of necitumumab

